9.1.10 Adverse Events

The investigator is responsible for reporting all AEs that are observed or reported during the study, regardless of their relationship to study treatment or their clinical significance.

9.1.10.1 Definition of Adverse Event

An AE is any untoward medical occurrence in a study patient administered a study treatment, whether or not considered drug related. This can be any unfavorable and unintended sign (such as an abnormal laboratory finding), symptom, or disease temporally associated with the use of a study treatment, without any judgment of causality.

The AE may be:

- A new illness;
- A worsening sign or symptom of the condition under treatment, or of a concomitant illness;
- An effect of the study medication, including comparator; or
- A combination of 2 or more of these factors.

No causal relationship with the study medication or with the clinical study itself is implied by the use of the term AE.

Surgical procedures themselves are not AEs; they are therapeutic measures for conditions that require surgery. The condition for which the surgery is required may be an AE. Planned surgical measures, if permitted by the clinical study protocol and the conditions leading to those measures are not AEs.

All AEs fall into the categories of "nonserious" or "serious" (Section 9.1.4).

9.1.11 Serious Adverse Events

9.1.11.1 Definition of Serious Adverse Event

An SAE is defined as any untoward medical occurrence that at any dose:

- Results in death;
- Is life threatening;
- Requires hospitalization or prolongation in existing hospitalization;
- Results in persistent or significant disability or incapacity; or
- Is a congenital anomaly or birth defect.

The term "life threatening" refers to an event in which the patient is at risk of death at the time of the event; it does not refer to an event, which hypothetically might have caused death if it were more severe.

Medical and scientific judgment should be exercised in deciding whether an AE is serious. Some important medical events that may not result in death, be life threatening, or require hospitalization may be considered SAEs when they may jeopardize the patient such that medical or surgical intervention is needed to prevent 1 of the outcomes previously listed. Examples of such medical events include intensive emergency treatment for an allergic reaction, blood dyscrasias or convulsions that do not result in inpatient hospitalization, and the development of drug dependency or drug abuse.

Visits to urgent care or emergency room facilities may not warrant reporting as SAEs unless the patient is admitted to the hospital or the event meets other "serious" criteria. Events that are not clearly meeting "serious" criteria can be discussed on a case by case basis with the Medical Monitor to help the investigator determine whether the event meets "serious" criteria.

If either the sponsor or principal investigator believes that any event is serious, the event must be considered and evaluated by the sponsor for possible expedited reporting.

Clarification of the difference between "serious" and "severe":

The term "severe" is often used to describe the intensity (severity) of a specific event (as in mild, moderate, or severe myocardial infarction); the event itself, however, may be of relatively minor medical significance (such as a severe headache). This is not the same as "serious," which is based on patient/event outcome or action criteria usually

associated with events that pose a threat to a patient's life or functioning. Seriousness (not severity) serves as a guide for defining regulatory reporting obligations.

9.2 Time Period and Frequency for Event Assessment and Follow-Up

For the purposes of this study, the period of observation extends from the time the patient gives his study-specific informed consent until the end of study procedures are completed.

If the investigator detects an SAE in a study patient after the end of the period of observation and considers the event possibly related to prior study treatment, he or she should contact the sponsor to determine how the AE should be documented and reported.

All AEs must be reported in detail on the appropriate page in the eCRF and followed to satisfactory resolution, until the investigator deems the event to be chronic or not clinically significant, or until the patient is considered to be stable.

A follow-up telephone call will be performed for those patients with an ongoing AE which the investigator believes to be not related to study treatment administration. A follow-up visit to the study site may occur for those patients with an ongoing AE which the investigator believes to be possibly related to study treatment administration.

All AEs must be reported in detail on the appropriate page in the eCRF and followed until they are resolved or stable, or judged by the investigator to be not clinically significant.

9.3 Characteristics of an Adverse Event

9.3.1 Relationship to Study Intervention

By definition, any AE that starts before the first dose of study treatment administration is considered to be "unrelated."

The investigator will assess the causality/relationship between the study treatment and the AE according to Appendix A (Schedule of Events). One of the following categories should be selected based on medical judgment, considering the following definitions and all contributing factors.

Category	Definition
Definitely related	A clinical event, including laboratory test abnormality, occurs in a plausible time relationship to treatment administration, and which concurrent disease or other drugs or chemicals cannot explain. The response to withdrawal of the treatment (dechallenge ¹) should be clinically plausible. The event must be definitive pharmacologically or phenomenologically, using a satisfactory rechallenge ² procedure if necessary.
Probably related	A clinical event, including laboratory test abnormality, with a reasonable time sequence to administration of the treatment, unlikely to be attributed to concurrent disease or other drugs or chemicals, and which follows a clinically reasonable response on withdrawal (dechallenge). Rechallenge information is not required to fulfill this definition.
Possibly related	A clinical event, including laboratory test abnormality, with a reasonable possibility that the adverse event may have been caused by the treatment. Information on treatment withdrawal may be lacking or unclear.
Unlikely to be related	A clinical event, including laboratory test abnormality, with a temporal relationship to treatment administration which makes a causal relationship improbable, and in which other drugs, chemicals or underlying disease provide plausible explanations.
Unrelated	A clinical event, including laboratory test abnormality, with little or no temporal relationship with treatment administration. May have negative dechallenge and rechallenge information. Typically, explained by extraneous factors (e.g., concomitant disease, environmental factors, or other drugs or chemicals).

 Table 9-1
 Causality Categories

¹ Dechallenge is when a drug suspected of causing an adverse event (AE) is discontinued. If the symptoms of the AE disappear partially or completely, within a reasonable time from drug discontinuation, this is termed a positive dechallenge. If the symptoms continue despite withdrawal of the drug, this is termed a negative dechallenge. Note that there are exceptions when an AE does not disappear upon discontinuation of the drug, yet drug-relatedness clearly exists (e.g., bone marrow suppression, fixed drug eruptions, tardive dyskinesia).

² Rechallenge is when a drug suspected of causing an AE in a specific patient in the past is readministered to that patient. If the AE recurs upon exposure, this is termed a positive rechallenge. If the AE does not recur, this is termed a negative rechallenge.

9.3.2 Expectedness of SAEs

The sponsor or designee will be responsible for determining whether an SAE is expected or unexpected. An adverse event will be considered unexpected if the nature,

severity, or frequency of the event is not consistent with the risk information previously described for the intervention as documented in the Investigator's Brochure.

9.3.3 Severity of Event

The investigator will assess all AEs for intensity (severity) in accordance with the following standard ratings (Table 9-2):

Table 9-2	Intensity Categories
-----------	----------------------

Category	Definition
Mild	Ordinarily transient symptoms, does not influence performance
	of patient's daily activities. Treatment is not ordinarily indicated.
Moderate	Marked symptoms, sufficient to make the patient
	uncomfortable. Moderate influence on performance of
	patient's daily activities. Treatment may be necessary.
Severe	Symptoms cause considerable discomfort. Substantial
	influence on patient's daily activities. May be unable to
	continue in the study and treatment may be necessary.
Life	Extreme limitation in activity, significant assistance required;
threatening	significant medical intervention/therapy required,
	hospitalization or hospice care probable.

When changes in the intensity of an AE occur more frequently than once a day, the maximum intensity for the event should be noted for that day. Any change in intensity of signs and symptoms over a number of days will be captured by recording a new AE, with the amended intensity grade and the date (and time, if known) of the change.

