9.4 Reporting Procedures

All AEs reported or observed during the study will be collected and recorded on the AE page of the eCRF for each patient from the date the ICF was signed until the end of their participation in the study, i.e., the patient has discontinued or completed the study.

Adverse events may be volunteered spontaneously by the patient, or discovered by the study staff during physical examinations or by asking an open, non-leading question such as, "How have you been feeling since you were last asked?" All AEs and any required remedial action will be recorded. The nature of the AE, date (and time, if known) of the AE onset, date (and time, if known) of the AE onset, date (and time, if known) of the AE outcome to date, severity, and action taken for the AE will be documented together with the investigator's assessment of the seriousness of the AE and causal relationship to study treatment and/or study procedure.

All AEs should be recorded individually in the study patient's own words (verbatim) unless, in the opinion of the investigator, the AEs constitute components of a recognized condition, disease or syndrome. In the latter case, the condition, disease or syndrome should be named rather than each individual symptom. The AEs will subsequently be coded using the latest version of Medical Dictionary for Regulatory Activities (MedDRA).

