12.4.4 Analysis of Primary and Key Secondary Efficacy Endpoints

The study is designed to evaluate the efficacy profile of ITI-007 60 mg based on the following primary and key secondary efficacy endpoints:

- Primary Endpoint Change from baseline to Day 43 in the MADRS total score.
- Key Secondary Endpoint Change from baseline to Day 43 in the CGI-BP-S score.

Safety Analyses

All safety parameters will be summarized using the safety analysis set.

Safety data such as reported and observed AEs, treatment emergent AEs (TEAEs) and SAEs, clinical laboratory results, vital signs, physical examinations and neurological findings, ECGs, and the different rating scales (YMRS, C-SSRS, AIMS, BARS, and SAS) will be summarized by treatment group and visit. When appropriate, out-of-range values

will be flagged in data listings and tabulated. Shift tables will be prepared for pre-specified safety measures, such as laboratory parameters, ECG and weight. Parameters collected in duplicate or triplicate will be analyzed as an average of the measures for the relevant time point, including baseline.

Reported AE terms will be coded using the latest version of the Medical Dictionary for Regulatory Activities (MedDRA). Treatment-emergent adverse events (TEAEs) will be defined as any AEs, regardless of the relationship to study drug, that occur or worsen in intensity after the first dose of study drug and on or before the date of last dose of study drug plus one day. Treatment-related TEAEs will be defined as any TEAEs that are considered by the investigator to be either possibly, probably, or definitely related to study drug. If relationship to study drug is missing, the TEAE will be considered as treatmentrelated. Severity of TEAEs will also be determined by the Investigator. All TEAEs, treatment-related TEAEs, and serious TEAEs will be summarized by treatment group, primary system organ class categories, and preferred terms. If a patient reports the same TEAE more than once within the same system organ class and preferred term, the event with the worst-case relationship to study drug will be used in the corresponding relationship summaries. Similarly, if a patient reports a TEAE more than once within the same system organ class and preferred term, the event with the worst case severity will be used in the corresponding severity summaries.

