16. SAFETY OUTCOMES

All outputs for safety outcomes will be based on the SAF Set.

16.1. FOR BY VISIT SUMMARIES OF CHANGE FROM BASELINE SUMMARIES, THE LAST VALUE ON TREATMENT (LAST ASSESSMENT ON OR BEFORE THE LAST DOSE OF STUDY MEDICATION PLUS ONE DAY) WILL BE PRESENTED. ADVERSE EVENTS

Adverse Events (AEs) will be coded using the Medical Dictionary for Regulatory Activities

Document: ...\ITI\ITI-007\MYA11638\Biostatistics\Documentation\SAP\ITI-007-404 SAP Final V1.0 12JUN2019.docx
Author: Version Number:1.0

Version Number:1.0
Version Date: 12JUN2019

Page 31 of 53

(MedDRA) central coding dictionary currently in effect at the time of analysis or database lock.

Treatment emergent adverse events (TEAEs) are defined as AEs that started or worsened in severity on or after the first dose of study medication and on or before the date last dose of study medication plus one day.

All AEs with an onset date after the last dose of study medication plus one day will be listed in the AE data listing and labelled as 'Follow-up Adverse Event'.

See APPENDIX 2 for handling of partial or completely missing dates for AEs. In the case where it is not possible to define an AE as treatment emergent or not due to missing dates, the AE will be classified as the worst case, i.e. treatment emergent.

An overall summary of number of subjects within each of the categories described in the subsections 16.1.1 and 16.1.2 below will be provided as specified in the TLF shells.

Listings will include all AEs, TEAEs and Non-TEAEs. A seperate listing for TEAEs leading to study discontinuation will be presented.

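### Read literally, an adverse event that began before dosing and only eases on treatment is counted as treatment-emergent, because a change in intensity is recorded as a new AE

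*Protocol*

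**What the plan says.** Protocol 9.3.3 (Severity of Event): "Any change in intensity of signs and symptoms over a number of days will be captured by recording a new AE". That record takes the revised grade and is dated when the grade changed. No direction is given, so improvement is covered. There is one exception: when intensity changes more than once a day, "the maximum intensity for the event should be noted for that day".

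Protocol 9.4 collects AEs "from the date the ICF was signed until the end of their participation in the study", so events during screening and washout are in the database.

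SAP 16.1 defines TEAEs as "AEs that started or worsened in severity on or after the first dose of study medication", with the window closing one day after last dose. The safety text under Protocol 12.4.4 is similar: AEs "that occur or worsen in intensity after the first dose of study drug".

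SAP 16.1.1 condenses repeated reports of the same PT and SOC within a subject to one for incidence counts. It then plans relative risks with 95% CIs and chi-square p-values for any TEAE and for each PT and SOC.

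Protocol 9.3.1 adds a causality rule tied to the start date: "any AE that starts before the first dose of study treatment administration is considered to be" unrelated.

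**The concern.** The TEAE definition has two limbs, *started* and *worsened*. The second exists so that a pre-dose event counts only if it gets worse on treatment. The recording rule in Protocol 9.3.3 undercuts this: every multi-day change of grade becomes a new AE with a new date, so an improvement can satisfy the *started* limb.

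Pre-dose events are foreseeable here. Patients stop antidepressants and other psychotropics during screening (Protocol 4 and 6.6). Headache, nausea, anxiety and insomnia could appear in that period, and Protocol 2.3.1 lists all four as side effects seen with ITI-007. At stake is whether the TEAE tables and their relative risks measure what their definition intends. The efficacy analysis is not touched.

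**Working it through.** **Inputs from the documents.** The recording rule and date of change (Protocol 9.3.3); collection from consent (Protocol 9.4); the TEAE window and two limbs (SAP 16.1); the PT/SOC condensing rule and relative risks (SAP 16.1.1). The plan states no figure that depends on this point, so there is none to reproduce.

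**Step 1: apply the rule to a test case.** The rule is: TEAE if first dose ≤ start ≤ last dose + 1 day, or if the AE worsened on or after first dose. Take dosing on Days 1 to 42, so the window is Days 1 to 43. A moderate headache starts on Day -5 and eases to mild on Day 6.

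| Record | Start | Grade | In window? | Worsened? | TEAE? |
|---|---|---|---|---|---|
| Original | Day -5 | Moderate | No | No | No |
| New | Day 6 | Mild | Yes | No | Yes, through *started* |

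**Step 2: look for a safeguard.** The PT/SOC condensing rule prevents double counting, but the Day 6 record is this subject's only TEAE record for that PT, so it stays. The worst-case rule in SAP 16.1 concerns missing dates, and here the dates are known. No visible text links the new record to the event it continues.

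**Step 3: illustrate the size.** Let p be the true TEAE rate for a term and f the added chance that a patient gains a spurious TEAE, taken as independent. Then

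observed rate = 1 − (1 − p)(1 − f).

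All rates are assumed: p = 10% on drug and 5% on placebo, a true relative risk of 2.00 and a true difference of 5.00 points.

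| f drug / f placebo | Drug | Placebo | RR | Difference |
|---|---|---|---|---|
| 1% / 1% | 1 − 0.90 × 0.99 = 10.9% | 1 − 0.95 × 0.99 = 5.95% | 1.83 | 4.95 points |
| 3% / 3% | 1 − 0.90 × 0.97 = 12.7% | 1 − 0.95 × 0.97 = 7.85% | 1.62 | 4.85 points |
| 5% / 1% | 1 − 0.90 × 0.95 = 14.5% | 1 − 0.95 × 0.99 = 5.95% | 2.44 | 8.55 points |

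Equal additions pull the ratio toward 1 and barely move the difference. Unequal additions can move both away from no effect, or the other way if placebo patients ease more often.

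**Step 4: test the proposed rule.** A record continuing a pre-dose AE is a TEAE only if its grade exceeds the last pre-dose grade.
- Moderate before dosing, mild on Day 6: mild does not exceed moderate, so not a TEAE.
- Mild before dosing, severe on Day 6: a TEAE, as now.
- Severe on Day -10, mild on Day -1, severe on Day 5: severe exceeds mild, so a TEAE. A threshold set at the *highest* pre-dose grade would wrongly drop this case.

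**The case against.** **The reading is not the only one.** Protocol 9.3.3 speaks of the date of the change and does not call it an onset date, while Protocol 9.4 lists onset date as a field of its own. The *worsened* limb would be nearly redundant if every re-graded record counted as having started, which suggests that easing events were not meant to count. A linking rule may also sit in SAP Appendix 2, the table shells, the study reference manual or the eCRF instructions, none of which can be read here. This stands as a reason for caution. It does not remove the point: the text that can be read calls the record a new AE, gives it only that date, and leaves the classification to whoever programs it.

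**The numbers are probably small.** To qualify, an event must be recorded before dosing, be at least moderate, last past first dose, and step down a grade while continuing. A mild event that simply resolves creates no new record. This stands.

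**Over-counting is conservative.** SAP 16.1 and 16.1.1 do lean to the worst case, but only for missing dates or a missing relationship. Over-counting is also not reliably conservative for a comparison between arms.

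**Stronger readings that a reader might infer.** The documents do not support any of these:
- *That the bias always runs toward 1 and would hide a drug excess.* This needs equal spurious rates in both arms. The mechanism is improvement, which may differ by arm; Protocol 2.3.1 reports sleepiness on ITI-007 at twice the placebo rate, so screening insomnia could ease more often on drug. Even with equal rates, the difference between arms is almost unchanged.
- *That related-TEAE counts are inflated.* The new record loses the automatic unrelated label of Protocol 9.3.1, but the investigator still judges causality and can call the tail of a pre-dose event unrelated or unlikely. Inflation is possible, not shown.
- *That follow-up AE rates are distorted.* A TEAE that eases more than one day after last dose gets a follow-up label, but SAP 16.1 uses that label only in a listing.

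**Conclusion.** The point holds as a conflict between a recording rule and an analysis definition. Applied as written, Protocol 9.3.3 and SAP 16.1 together class an easing pre-dose AE as treatment-emergent, contrary to the evident purpose of the *worsened* limb, and no visible rule corrects it. The misclassified records enter the TEAE incidence tables and the relative risks in SAP 16.1.1.

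The number of patients affected cannot be computed from the documents and is probably small; the direction of any bias is unknown. The illustrated relative risks of 1.83, 1.62 and 2.44 against a true 2.00 rest wholly on assumed rates and on independence. The conclusion also assumes that no linking rule exists in the material that cannot be read. If one does, SAP 16.1 need only cite it. It is worth correcting because these tables carry confidence intervals and p-values and the correction is cheap.

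**What to change.** In SAP 16.1, state that a record on or after first dose that continues a pre-dose AE (same PT with adjoining dates, or an eCRF link) is treatment-emergent only if its intensity exceeds the last intensity recorded before first dose. All other new onsets count as they do now.

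Optionally, add an eCRF field linking the new record to its parent AE. The new record should keep the date of change as its own date. If it carried the original onset date instead, a pre-dose AE that worsens on drug would become unrelated by definition under Protocol 9.3.1, and a possible drug signal would be lost.

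The cost is one SAP sentence and a small derivation in the AE dataset; matching on PT and adjoining dates needs no new data. TEAE counts will be slightly lower. An event that eases on treatment and then returns only to its last pre-dose grade would not count, which the SAP should say openly. Matching on PT and dates may occasionally join two separate episodes; the link field would avoid that.

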9.4 Reporting Procedures

All AEs reported or observed during the study will be collected and recorded on the AE page of the eCRF for each patient from the date the ICF was signed until the end of their participation in the study, i.e., the patient has discontinued or completed the study.

Adverse events may be volunteered spontaneously by the patient, or discovered by the study staff during physical examinations or by asking an open, non-leading question such as, "How have you been feeling since you were last asked?" All AEs and any required remedial action will be recorded. The nature of the AE, date (and time, if known) of the AE onset, date (and time, if known) of the AE onset, date (and time, if known) of the AE outcome to date, severity, and action taken for the AE will be documented together with the investigator's assessment of the seriousness of the AE and causal relationship to study treatment and/or study procedure.

All AEs should be recorded individually in the study patient's own words (verbatim) unless, in the opinion of the investigator, the AEs constitute components of a recognized condition, disease or syndrome. In the latter case, the condition, disease or syndrome should be named rather than each individual symptom. The AEs will subsequently be coded using the latest version of Medical Dictionary for Regulatory Activities (MedDRA).

